3.4.3 Exclusion Criteria

Subjects will be excluded if they meet any of the exclusion criteria in [Table 3.4.3-1](#).

Table 3.4.3-1 Exclusion Criteria	
1.	Females who are breast-feeding and/or who have a positive pregnancy test result prior to receiving IMP.
2.	Liver function tests including AST, ALT \geq 1.5 \times ULN.
3.	Nocturnal enuresis.
4.	Need for chronic diuretic use.
5.	Subjects with advanced diabetes (eg, glycosylated hemoglobin [HgbA1c] $>$ 7.5, and/or glycosuria by dipstick, significant proteinuria, retinopathy), evidence of additional significant renal disease(s) (ie, currently active glomerular nephritides), renal cancer, single kidney, or recent (within 6 months of screening) renal surgery or acute kidney injury.
6.	Subjects who have known clinically significant allergic reactions to chemicals with structure similar to tolvaptan (ie benzazepines): benzazepril, conivaptan, fenoldopam mesylate or mirtazapine.
7.	Subjects having disorders in thirst recognition or inability to access fluids.

Table 3.4.3-1 Exclusion Criteria	
8.	Subjects who have bladder dysfunction and/or difficulty voiding.
9.	Subjects with critical electrolyte imbalances, as determined by the investigator.
10.	Subjects with or at risk of significant hypovolemia, as determined by investigator.
11.	Subjects with a history of substance abuse (within the last 6 months).
12.	Subjects 12 years of age and older having contraindications to, or interference with MRI assessments (eg, ferro-magnetic prostheses, aneurysm clips, severe claustrophobia).
13.	Subjects taking a vasopressin agonist (eg, desmopressin).
14.	Subjects with a history of persistent noncompliance with antihypertensive or other important medical therapy.
15.	Subjects taking medications or having concomitant illnesses likely to confound endpoint assessments, including taking approved (ie, marketed) therapies for the purpose of affecting PKD cysts such as tolvaptan, vasopressin antagonists, anti-sense RNA therapies, rapamycin, sirolimus, everolimus, or somatostatin analogs (ie, octreotide, sandostatin).
16.	Has any medical condition that, in the opinion of the investigator, could interfere with evaluation of the trial objectives or safety of the subjects.
17.	Is deemed unsuitable for trial participation in the opinion of the investigator.
18.	Subjects who received any investigational agent in a clinical trial within 30 days prior to screening.
19.	Subjects who have a known lactose intolerance.

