5.4.2 Requirements for Repeated Liver Testing

5.4.2.1 Liver Transaminase Elevations

Management of abnormal liver function test results should be based on the investigator's clinical judgment. The appearance of any suspicious symptom or sign should trigger prompt testing of hepatic function (ie, within 48 to 72 hours). A liver function test result that is $2 \times$ ULN is generally accepted as a clinically significant occurrence across various medical disciplines.

For a subject who experiences an elevation in AST or ALT that is $\geq 2 \times$ ULN or whose levels increase \geq 2 times their initial baseline value in subjects with an elevated baseline value, a BT level should also be evaluated. Elevated values should be confirmed via retest within 48 to 72 hours.

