5.4.2.2 Guidelines for Repeat Liver Testing in Subjects with Normal Values at Screening

The appearance of any suspicious symptom or sign should trigger prompt testing of hepatic function (ie, within 48 to 72 hours). Local laboratory testing is acceptable, ideally with a concurrent central laboratory sample for confirmation.

Any transaminase or bilirubin values which exceed $2 \times$ ULN should also prompt immediate retesting within 48 to 72 hours. While values remain in an abnormal range, testing frequency should be increased to at least weekly for the first month, gradually returning to monthly as indicated by the results.

If hepatic injury is suspected, tolvaptan should be promptly discontinued, appropriate treatment should be instituted, and investigations should be performed to determine probable cause. Such an event should be reported and followed until resolution.

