5.4.2.3 Subjects with Elevated Liver Transaminase at Screening

Subjects found to have liver laboratory abnormalities at screening or who have a history of non-ADPKD-related liver disease will require further evaluation. These subjects will need to have the special liver eCRF (see [Section 5.4.5](#)) completed and additional testing

Protocol 156-12-298

will be required during screening to confirm the stability of the abnormality prior to randomization to confirm eligibility. Management of such subjects should be closely coordinated with the trial's medical monitor. In these subjects, further changes in liver test levels of $> 2 \times$ upper limit of their highest screening value at any point postscreening should prompt re-testing within 48 to 72 hours. Should such an increase occur during treatment with IMP, the subject will be immediately discontinued from treatment. IMP should not be resumed until monitoring indicates abnormalities have resolved, are stable or are not rapidly increasing, and then only with an increased frequency of monitoring.

Protocol 156-12-298

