5.4.3 Guidelines for Repeat Testing of Liver Transaminases

The following guideline for repeat testing may be used by investigators as a reference for any subject with an ALT or AST $\geq 2 \times$ ULN:

- ALT, AST, ALP, and BT should be repeated within 48 to 72 hours (needed to confirm abnormalities and determine if they are increasing or decreasing).
- Inquiries should be made about symptoms (fatigue, nausea, vomiting, right upper quadrant pain or tenderness, fever, and/or rash) and signs like jaundice or yellowish discoloration of sclera.
- Close observation is required if symptoms persist or repeat testing shows ALT or AST $\geq 3 \times$ ULN for subjects with normal baseline measures OR 2-fold increases above baseline values for subjects with elevated values before drug exposure. If close monitoring is not possible, the drug should be interrupted until such monitoring is possible or the drug should be permanently discontinued.
- All trial subjects with evidence of possible DILI should be followed until all abnormalities return to normal or to the baseline state.

Close observation may involve:

- Repeating liver enzymes and serum bilirubin tests 2 or 3 times weekly.
- Frequency of retesting can decrease to once a week or less if abnormalities stabilize or if the trial drug has been interrupted/discontinued and the subject is asymptomatic.
- Obtaining a more detailed history of symptoms and prior or concurrent diseases.
- Obtaining a history of concomitant drug use (including nonprescription medications and herbal and dietary supplement preparations), alcohol use, recreational drug use, special diets, and change in diet.
- Ruling out acute viral hepatitis types A, B, C, D, and E; autoimmune or alcoholic hepatitis, nonalcoholic steatohepatitis; hypoxic/ischemic hepatopathy, and biliary tract disease.
- Obtaining a history of exposure to environmental chemical agents.
- Obtaining additional tests to evaluate liver function, as appropriate (eg, international normalized ratio [INR], direct bilirubin).
- Considering gastroenterology or hepatology consultations.

5.4.4 Liver Test Abnormalities and Interruption/Discontinuation of Investigational Medicinal Product

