Liver transaminase or bilirubin levels reaching or exceeding $2 \times$ ULN that have an uncertain or rapidly increasing trajectory should prompt at least temporary IMP interruption. IMP should not be resumed until monitoring indicates abnormalities have resolved, are stable or are not rapidly increasing, and then only with an increased frequency of monitoring.

Protocol 156-12-298

A subject must be discontinued from the trial on confirmation of any of the following criteria:

- ALT or AST $\geq 8 \times$ ULN
- ALT or AST $\geq 5 \times$ ULN for more than 2 weeks
- ALT or AST $\geq 3 \times$ ULN and (BT $\geq 2 \times$ ULN or INR > 1.5)
- ALT or AST $\geq 3 \times$ ULN with appearance of fatigue, nausea, vomiting, right upper quadrant pain or tenderness, fever, rash, and/or eosinophilia ($> 5\%$) and signs of jaundice

If an investigator has any question about how to proceed with a particular subject's case, he/she should contact the regional medical monitor to discuss. The United States Food and Drug Administration (US FDA) has issued a guidance for industry regarding this topic. The sponsor is integrating many of the recommendations in this guidance into all of its clinical research programs. Links to this guidance and information from the FDA regarding DILI are provided in the references.^{14,15}

5.4.5 Requirements for Special Reporting Using the Liver Disease Electronic Case Report Form and Immediately Reportable Event Form

The purpose of the liver disease eCRF and optional additional testing is to facilitate review of each subject who presents with, or develops, a liver abnormality during the trial or and to determine the probable cause(s) of these abnormalities. The review will be performed by a blinded, independent, hepatic, adjudication committee using Drug Induced Liver Injury Network (DILIN) probability criteria.¹⁶

- $< 25\%$ = unlikely
- 25% to 50% = possibly
- 51% to 75% = probably
- 76% to 95% = very likely
- $>95\%$ = definite

The result of these analyses may be presented separately from the CSR.

The investigator must complete a special liver disease eCRF and IRE for any subject who:

- 1) Discontinues treatment due to a liver-related AE,
- 2) Reports a serious liver-related AE,
- 3) With normal screening levels develops ALT or AST levels $\geq 3 \times$ ULN,
- 4) With normal screening levels develops BT levels $\geq 2 \times$ ULN, or

Protocol 156-12-298

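### Criterion 4 of the mandatory liver stopping list (Protocol 5.4.4), read literally, requires jaundice as well as symptoms, so a symptomatic child without jaundice whose bilirubin and INR stay below their limits has no mandatory permanent stop at ALT/AST 3 to <5 × ULN, or at 5 to <8 × ULN for up to 2 weeks

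*Protocol*

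**What the plan says.** The mandatory list in Protocol 5.4.4 is introduced by "A subject must be discontinued from the trial on confirmation of any of the following criteria". The criteria are:

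1. ALT or AST ≥8 × ULN.
2. ALT or AST ≥5 × ULN for more than 2 weeks.
3. ALT or AST ≥3 × ULN with total bilirubin (BT) ≥2 × ULN or INR >1.5.
4. ALT or AST ≥3 × ULN with any of a set of symptoms (fatigue, nausea, fever and rash are among them) and/or eosinophilia above 5%, "and signs of jaundice".

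Just before the list, 5.4.4 says that transaminases or bilirubin at or above 2 × ULN with an "uncertain or rapidly increasing trajectory should prompt at least temporary IMP interruption".

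Section 5.4.2.3 covers children with liver abnormalities at screening or a history of non-ADPKD liver disease. If a test rises above 2 × the highest screening value on treatment, "the subject will be immediately discontinued from treatment". IMP may be resumed once the abnormality has resolved, is stable or is not rising rapidly.

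Section 3.8.3.3 sends the reader to 5.4.2.3 for the permanent-discontinuation criteria, although that list is in 5.4.4.

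**The concern.** Within one sentence, criterion 4 closes its symptom list with *and/or* and then attaches jaundice with a bare *and*. Taken at its word, the rule does not act on symptoms alone. It waits for a sign that usually accompanies raised bilirubin, which criterion 3 already covers.

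Long-term safety is the primary objective. Protocol 1.3 names liver toxicity as the most notable safety issue of chronic tolvaptan use and reports 3 adults with potentially serious drug-induced liver injury. A mandatory stopping rule should give the same answer at every site, and here two sites could read the same sentence and treat the same child differently.

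Two features of the plan make the wording matter more. INR is not in the required laboratory panel (Table 3.7.4.2-1) and appears in 5.4.3 only as an additional test, so that arm of criterion 3 may go unmeasured. Under the COVID-19 addendum, remote Phase B visits replace the directed physical examination with a telephone interview, where symptoms are easier to establish than jaundice.

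**Working it through.** The plan has no figure to reproduce here. The check is a logical one, in three steps.

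**Step 1: apply the four criteria to one child.** Take a symptomatic child without jaundice, with BT 1.9 × ULN and INR 1.5, just inside the limits of criterion 3. *More than 2 weeks* is taken as more than 14 days.

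| ALT/AST (× ULN) | Days at that level | Criterion 4 with *and* | Criterion 4 with *and/or* |
|---|---|---|---|
| 2.9 | 1, 14, 15 | no stop | no stop |
| 3 and 4.9 | 1, 14, 15 | no stop | stop (criterion 4) |
| 5 and 7.9 | 1, 14 | no stop | stop (criterion 4) |
| 5 and 7.9 | 15 | stop (criterion 2) | stop (criteria 2 and 4) |
| 8 | 1, 14, 15 | stop (criterion 1) | stop (criteria 1 and 4) |

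The uncovered region is therefore 3 to <5 × ULN without time limit, and 5 to <8 × ULN for up to 2 weeks.

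**Step 2: count the combinations under 5.4.4 alone.** At ALT/AST ≥3 × ULN use four bands: 3 to <5; 5 to <8 for up to 2 weeks; 5 to <8 for longer; ≥8. Cross them with four yes/no items: BT ≥2 × ULN, INR >1.5, symptom or eosinophilia, jaundice.

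- Total: 4 × 2 × 2 × 2 × 2 = 64.
- Criteria 1 and 2 stop the two upper bands: 2 × 16 = 32.
- Criterion 3 stops three quarters of the other 32: 24.
- Left for criterion 4: 64 − 32 − 24 = 8 (two bands × symptom yes/no × jaundice yes/no).
- With *and*, criterion 4 stops 2 of the 8 and leaves 6. With *and/or* it stops 6 and leaves 2.
- Of the 6 left by *and*, 2 have symptoms without jaundice, 2 have jaundice without symptoms and 2 have neither.

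Now assume that jaundice implies BT ≥2 × ULN, which the documents do not state. The 16 combinations with jaundice and lower BT drop out, leaving 48. Criteria 1 to 3 stop 44 and leave 4. Criterion 4 stops none of the 4 with *and*, and 2 with *and/or*.

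These are rule combinations, not patients.

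**Step 3: look for another mandatory stop.**

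| Section | What it offers the symptomatic child without jaundice | Force |
|---|---|---|
| 5.4.2.1 | "Management of abnormal liver function test results should be based on the" investigator's judgment | discretionary |
| 5.4.2.2 (normal screening values) | "If hepatic injury is suspected, tolvaptan should be promptly discontinued" | *should*; depends on suspicion, no defined trigger |
| 5.4.3 | close observation; interrupt or stop if monitoring is not possible | offered as a reference guideline |
| 5.4.4, before the list | temporary interruption from 2 × ULN | *should*; depends on trajectory |
| 3.8.3.3 | clinical signs of liver injury, with right upper quadrant pain as an example | *may* |
| 5.4.2.3 | stop above 2 × highest screening value | firm but reversible; only with abnormal screening tests or a history of non-ADPKD liver disease |

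For a child covered by 5.4.2.3, that reversible stop already applies in the gap. Exclusion criterion 2 in Table 3.4.3-1 ("Liver function tests including AST, ALT" ≥1.5 × ULN) keeps every screening transaminase below 1.5 × ULN, so the threshold is below 2 × 1.5 = 3 × ULN. The synopsis gives the exclusion as >1.5 × ULN. On that version a child at exactly 1.5 would have a threshold of >3.0 × ULN, an edge case of no practical weight. The criterion 4 ambiguity about a permanent stop still applies to these children.

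**The case against.** The strongest reply is that the child is not left without a route off treatment. Section 5.4.2.2 is written for children with normal screening values, and ALT or AST at 3 × ULN with right upper quadrant pain is an obvious reason to suspect liver injury. A newly found rise often has an uncertain trajectory, which should prompt interruption. Section 5.4.3 calls for close observation, and 5.4.4 directs questions to the medical monitor. All of this stands, and many investigators would stop. None of it is mandatory, and a symptomatic child with a stable value near 4 × ULN need not trigger the trajectory rule.

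A second reply is that either reading weakens the point. Section 5.4.3 has a similar list ending "and signs like jaundice or yellowish discoloration of sclera", where *and* only adds an item to ask about; if 5.4.4 means the same, this is loose drafting. If *and* is deliberate, the protocol has a coherent tier: observe for symptoms, stop for jaundice. The documents do not settle which was meant, and that is the reason to clarify a mandatory sentence.

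Readers might infer three stronger things that the documents do not support:

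- *That this is the only unprotected group.* It is not. Asymptomatic children in the same ALT/AST ranges, with BT and INR below their limits, have no mandatory permanent stop under either wording. Under the literal wording, neither do jaundiced children without symptoms if BT is <2 × ULN.
- *That the sponsor intended symptoms alone to be insufficient.* The parallel in 5.4.3 points the other way, and 3.8.3.3 gives jaundice and right upper quadrant pain as separate examples.
- *That liver events would be missed.* Under 5.4.5, ALT or AST ≥3 × ULN from normal screening values, or a rise above 2 × the highest screening value from abnormal ones, still triggers the liver case report form and immediate reporting, for review by the hepatic adjudication committee.

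**Conclusion.** The point holds as an ambiguity in a mandatory safety rule. It does not show that children are left without any means of stopping. On the literal wording, and given BT <2 × ULN and INR ≤1.5, the affected region is two of the eight combinations that reach criterion 4: symptoms or eosinophilia without jaundice, in each of the two lower ALT/AST bands. The finding that criterion 4 adds nothing to criterion 3 rests on the assumption that jaundice implies BT ≥2 × ULN. Without it, the literal criterion adds only children with both symptoms and jaundice at lower bilirubin.

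How many children this concerns cannot be derived from the documents. The correction is worth making because liver safety is central to the trial and the change is very small. Confidence is moderate, since the intended meaning is probably the one the fix would state.

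**What to change.** By amendment:

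1. In criterion 4 of 5.4.4, join the jaundice clause with *and/or* in place of *and*.
2. In the sentence introducing the list, make the action permanent discontinuation of IMP instead of discontinuation from the trial, with follow-up continuing under 3.8.3.2. This is a separate gain. Section 5.4.3 wants every child with possible drug-induced liver injury followed until values return to normal or baseline, and a wider criterion should not take children out of observation.
3. In 3.8.3.3, change the reference for the permanent-discontinuation criteria from 5.4.2.3 to 5.4.4 (clerical).

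No new tests are needed. The cost is that some children with fever, nausea, fatigue or rash from a non-drug cause, and confirmed ALT or AST ≥3 × ULN, would come off IMP permanently when they might have stayed on under close observation. The change is not meant to add a stop for asymptomatic children. Amendment 2 states that Phase A assessments were complete, so a later change helps Phase B only.

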5.5 Pregnancy

For the purposes of this pediatric trial, women of childbearing potential (WOCBP) are defined as female subjects ≥ 12 years of age and all female subjects < 12 years of age, if menstruation has started.

For WOCBP and for men who are sexually active, there must be a documented agreement that the subject and/or their partner will take effective measures (eg, double-barrier method) to prevent pregnancy during the course of the trial and for 30 days after the last dose of IMP. Unless the subject is sterile (ie, women who have had a bilateral oophorectomy and/or hysterectomy or who have been postmenopausal for at least 12 consecutive months; or men who have had a bilateral orchidectomy) or remains fully abstinent; 2 of the following precautions must be used: vasectomy, tubal ligation, vaginal diaphragm, intrauterine device, birth control pills, birth control depot injection, birth control implant, condom with spermicide, or sponge with spermicide. Any single method of birth control, including vasectomy and tubal ligation, may fail, leading to pregnancy. Periodic abstinence (eg, calendar, ovulation, symptothermal, postovulation methods) or withdrawal are not acceptable methods of contraception. The contraceptive method will be documented at each trial visit.

Before enrolling females of childbearing potential in this clinical trial, investigators must review the below guidelines about trial participation with all WOCBP. Investigator (or appropriate site staff) is advised to counsel participants on the risk of pregnancy while participating in a clinical trial as well as ensuring the child understand how pregnancies occur and can be avoided. This should be documented in source records. The topics should generally include:

- General information
- Informed consent form
- Pregnancy prevention information

Protocol 156-12-298

- Drug interactions with hormonal contraceptives
- Contraceptives in current use
- Guidelines for the follow-up of a reported pregnancy

Before trial enrollment, females of childbearing potential must be advised of the importance of avoiding pregnancy during trial participation and the potential risk factors for an unintentional pregnancy. The subject or the subject's parent/legal guardian or legally acceptable representative must sign an ICF stating that the above-mentioned risk factors and the consequences were discussed with the subject and/or the parent/legal guardian or legally acceptable representative.

A urine and/or serum pregnancy test for human chorionic gonadotropin will be performed at screening on all females of childbearing potential. If a urine test is performed and is positive, the investigator will follow-up with a confirmatory serum test.

During the trial, all females of childbearing potential should be instructed to contact the investigator immediately if they suspect they might be pregnant (eg, missed or late menstrual cycle).

If a subject is suspected to be pregnant before she receives IMP, the IMP administration must be withheld until the results of serum pregnancy tests are available. If the pregnancy is confirmed, the subject must not receive the IMP and must not be enrolled in the trial. If pregnancy is suspected while the subject is taking IMP, the IMP must be withheld immediately (if reasonable, taking into consideration any potential withdrawal risks) until the result of the pregnancy test is known. If pregnancy is confirmed, the IMP will be permanently discontinued in an appropriate manner (eg, dose tapering if necessary for subject safety) and the subject will be withdrawn from the trial.

The investigator must immediately notify the sponsor of any pregnancy associated with IMP exposure during the trial and for 30 days after the last dose of IMP, and record the event on the IRE form and forward it to the sponsor. The sponsor will forward Pregnancy Surveillance Form(s) for monitoring the outcome of the pregnancy.

Protocol required procedures for trial discontinuation and follow-up must be performed on the subject unless contraindicated by pregnancy (eg, x-ray studies). Other appropriate pregnancy follow-up procedures should be considered, if indicated. In addition, the investigator must report to the sponsor, on appropriate Pregnancy Surveillance Form(s), follow-up information regarding the course of the pregnancy, including perinatal and neonatal outcome. Infants will be followed for a minimum of 6 months from the date of birth.

Protocol 156-12-298

